Appendix 2 12-Week Safety Follow-Up (OLE, Part 1) Schedule of Assessments

Part 1 (OLE)	Week (± 7 days)		Unscheduled Visit ^c
	6 ^a	12/Early Withdrawal Visit ^b	
Concomitant medications	x	x	x
Adverse events	x	x	x
Urine pregnancy test ^d		x	
Anti-therapeutic antibody sample (serum) ^e		x	
PML assessment interview ^f		x	x ^g
Neurological examination ^{f, h}		x	x ^g

ATA = anti-therapeutic antibody; JCV = John Cunningham virus; OLE = open-label extension; PML = progressive multifocal leukoencephalopathy.

- ^a Week 6 study assessments are to be made by telephone visit and not by clinic visit.
- ^b If the patient discontinues prior to completion of the 12-week safety follow-up, the indicated assessments for the 12-week safety follow-up clinic visit should be performed as the Early Withdrawal visit of the safety follow-up period.
- ^c Unscheduled visit for safety monitoring.
- ^d For women of childbearing potential, including those who have had a tubal ligation, perform a urine pregnancy test; if the urine pregnancy test result is positive, confirm with a serum pregnancy test.
- ^e If serum sickness or a clinically significant allergic drug reaction is suspected, Sponsor should be notified and serum for ATAs should be drawn and sent to the central laboratory. ATA samples may be used for assessment of etrolizumab serum concentration.
- ^f Administer before other assessments.
- ^g If clinically indicated.
- ^h Neurologic examination consists of the PML Subjective Checklist and the PML Objective Checklist, as per [Appendix 8](#).

Appendix 3 Extended Progressive Multifocal Leukoencephalopathy Safety Monitoring (SM, Part 2) Schedule of Assessments

Part 2 (SM)	92-week Extended PML Monitoring Period ^a
	24, 48, 68, and 92 Weeks after Patient Discontinuation from Study OR Early Termination ^b
PML Subjective Checklist (Telephone Only) ^c	X
Adverse Event Reporting to Roche Safety Risk Management ^d	X

OLE-SM=open-label extension–safety monitoring; PML=progressive multifocal leukoencephalopathy; SM=safety monitoring.

Note: The extended PML monitoring period is to be conducted for patients completing or discontinuing from Part 1 (OLE) of the OLE-SM study AND for patients entering OLE-SM Part 2 (SM) from Study GA29144 after completion of 12-week safety follow-up in Study GA29144.

- ^a The total length of the PML monitoring period is 104 weeks after the patient discontinues from the study (12-week safety follow-up plus 92-week extended PML monitoring period). During the extended PML monitoring period telephone visits will occur at the indicated timepoints for the 92-week extended PML monitoring period. The extended PML monitoring will be conducted using a PML Subjective Checklist over the telephone. PML monitoring should occur within 7 days of the specified day.
- ^b If the patient discontinues after the 12-week safety follow-up visit but prior to study completion (end of extended PML monitoring period), the early termination visit from the extended PML monitoring period should be performed (a subjective checklist by telephone).
- ^c If there are any signs or symptoms suggestive of PML during the telephone visit, the patient will be asked to come into the clinic for a neurologic examination (see Section 4.4.5).
- ^d Investigators are not required to actively monitor patients for adverse events; however, if they become aware of any deaths, serious adverse events, or non-serious adverse events of special interest, these should be reported directly to the Sponsor via telephone or via fax machine using the Serious Adverse Event Reporting Form and fax cover sheet (see "Protocol Administrative and Contact Information & List of Investigators").

Appendix 4

Childbearing Potential, Pregnancy Testing, and Contraception

All women of childbearing potential (including those who have had a tubal ligation) will have a serum pregnancy test at screening and a urine pregnancy test prior to administration of study drug at subsequent visits. If a urine pregnancy test result is positive, study drug will not be administered that day. The result must be confirmed by a serum pregnancy test (conducted by the central laboratory). Refer to Section 5.5.3 of the protocol for management of a patient with a confirmed pregnancy.

A woman is considered to be of childbearing potential if she is postmenarcheal, has not reached a postmenopausal state (≥ 12 months of amenorrhea with no identified cause other than menopause), and has not undergone surgical sterilization (removal of ovaries and/or uterus).

For women: patients are considered to be of childbearing potential unless they meet one of the following criteria:

- The patient has been postmenopausal (non–therapy-induced amenorrhea) for at least 12 months
- The patient had a surgical bilateral oophorectomy (with or without hysterectomy) more than 6 weeks prior to enrollment
- The patient had a hysterectomy

Female patients of reproductive or childbearing potential who are unwilling to use a highly effective method of contraception or remain abstinent during the treatment period and for at least 24 weeks after the last dose of study drug will be excluded from study participation.

Abstinence is acceptable only if it is in line with the preferred and usual lifestyle of the patient. Periodic abstinence (e.g., calendar, ovulation, symptothermal, or postovulation methods) and withdrawal are not acceptable methods of contraception.

Examples of highly effective contraception include the following:

- Combined oral contraception pill
- Contraceptive transdermal patch
- Intrauterine device
- Implants for contraception
- Injections for contraception (with prolonged release)
- Hormonal vaginal device
- Sterilization, surgical tubal ligation
- Sole sexual partner consisting of surgically sterilized male partner with appropriate postsurgical verification of the absence of spermatozoa in the ejaculate

Appendix 4

Childbearing Potential, Pregnancy Testing, and Contraception (cont.)

- Double-barrier methods: condom and occlusive cap (diaphragm or cervical/vault caps) with spermicidal foam/gel/film/cream/suppository (Note: a female condom and male condom should not be used together as friction between the two can result in either product failing)

Patients may provide verbal confirmation that the partner completed appropriate follow-up after vasectomy. Sites are not required to obtain partner medical records.

For men: agreement to remain abstinent (refrain from heterosexual intercourse) or use contraceptive measures and agreement to refrain from donating sperm, as defined below:

With female partners of childbearing potential or pregnant female partners, men must remain abstinent or use a condom during the treatment period and for at least 24 weeks after the last dose of study drug. Men must refrain from donating sperm during this same period.

For men and women: The reliability of sexual abstinence should be evaluated in relation to the duration of the clinical trial and the preferred and usual lifestyle of the patient. Periodic abstinence (e.g., calendar, ovulation, symptothermal, or postovulation methods) and withdrawal are not acceptable methods of contraception.

Appendix 5 Crohn's Disease Activity Index

[figure not shown]
Category	Count	Initial Total	Multiplication Factor	Total
Number of liquid or very soft stools	7-day total number of liquid or very soft stools (reported on the 7 days immediately prior to the study visit)		x 2	
Abdominal pain	7-day total of daily abdominal pain scores on a 3-point scale: 0=none, 1=mild, 2=moderate, 3=severe (reported on the 7 days immediately prior to the study visit)		x 5	
General well being	7-day total of daily general well-being scores on a 4-point scale: 0=generally well, 1=slightly under par, 2=poor, 3=very poor, 4=terrible (reported on the 7 days immediately prior to the study visit)		x 7	
Extra-intestinal manifestations of Crohn's Disease	Total number of checked boxes (check all that apply):  Arthritis/arthralgia  Iritis/uveitis  Erythema nodosum/pyoderma gangrenosum/apthous stomatitis  Anal fissure, fistula, or abscess  Other fistula  Fever over 37.8°C during past week		x 20	
Lomotil/Imodium/opiates for diarrhea	Yes = 1 No = 0		x 30	
Abdominal mass	None = 0 Questionable = 2 Definite = 5		x 10	
Hematocrit (%) ^a	Males: subtract value from 47 Females: subtract value from 42		x 6	
Body Weight ^b	(1- (Body weight/Standard Weight)) x 100		x 1	
Final Score			Add totals:	

^a If hematocrit subtotal <0, enter 0.
^b If body weight subtotal < -10, enter -10.

Adapted from: Best WR, Beckett JM, Singleton JW, Kern F, Jr. Development of a Crohn's disease activity index. National Cooperative Crohn's Disease Study. *Gastroenterology* 1976;70(3):439-44.

Appendix 6
Abdominal Pain Questionnaire (APQ)

Please rate your worst abdominal pain over the past 24 hours:

Appendix 7 Bristol Stool Form Scale

THE BRISTOL STOOL FORM SCALE

Type 1		Separate hard lumps, like nuts (hard to pass)
Type 2		Sausage-shaped but lumpy
Type 3		Like a sausage but with cracks on its surface
Type 4		Like a sausage or snake, smooth and soft
Type 5		Soft blobs with clear-cut edges (passed easily)
Type 6		Fluffy pieces with ragged edges, a mushy stool
Type 7		Watery, no solid pieces ENTIRELY LIQUID

Reproduced by kind permission of [name],
Reader in Medicine at the University of Bristol.
©2000 Produced by Norgine Pharmaceuticals Limited.

Appendix 8 Worksheet for the PML Neurologic Examination

PML Subjective and Objective Checklists of neurologic assessments to monitor for progressive multifocal leukoencephalopathy (PML) in the Etralizumab Phase III Studies

PML usually manifests with subacute, progressive neurologic deficits including:

Neurologic Domain	Signs/Symptoms	Relevant PML Subjective/Objective Checklist Question
Altered mental status	Can encompass a variety of presenting signs and symptoms including cognitive changes (confusion, difficulty concentrating, memory loss) and altered behavior (including personality changes)	Q2, Q5, Q6
Higher cortical dysfunction	Impaired comprehension and/or formulation of language (aphasia), loss of ability to recognize objects, persons, sounds, shapes, or smells (agnosia)	Q2, Q5, Q6
Visual changes	Loss of visual fields (homonymous hemianopsia), double vision (diplopia)	Q1
Motor deficits	Weakness (hemiparesis or monoparesis), seizures (generalized or partial), difficulties with speech (dysarthria) or swallowing (dysphagia)	Q2, Q3
Sensory deficits	Sensory loss (i.e. paresthesia)	Q7
Coordination	Difficulty walking and maintaining balance (ataxia), lack of voluntary coordination of limb movement (limb ataxia)	Q4

In order to monitor patients for PML, a neurologic exam (including evaluation of cranial nerves, motor and sensory function, coordination, and mental status) will be performed as per the Schedules of Assessments (see [Appendix 1](#)). This neurologic exam will consist of administration of the PML Subjective Checklist and the PML Objective Checklist.

At screening, the PML Subjective Checklist and the PML Objective Checklist (including the components listed as optional, e.g. muscle group strength testing, recall of 3 objects in 1 minute, and sensory testing) should be performed.

At all other visits, the PML Subjective Checklist and the PML Objective Checklist (bolded items) should be performed, and the optional items should only be performed when there is an abnormal finding on the corresponding PML Subjective Checklist (i.e., complaints of focal weakness or focal sensory change would prompt a more detailed objective neurologic evaluation).

Appendix 8 Worksheet for the PML Neurologic Examination (cont.)

PML Subjective Checklist

Symptoms	“Compared to how you usually feel, have you had a significant change in any of the following?”		If the answer is “Yes”, obtain a description of the symptom(s) with examples	Applicable Objective Test(s): Document result on PML Objective Checklist Worksheet
	YES	NO		
1. Have you been experiencing any persistent difficulty with your vision such as loss of vision or double vision? Have you been having trouble with reading?				
 • Test visual fields and ocular motility
2. Have you been experiencing any persistent difficulty speaking or having your speech understood by others?				
 • Casual observation of speech output for dysarthria or aphasia.
3. Have you been experiencing any persistent weakness in an arm or a leg?				
 • Test for pronator drift (Barre maneuver). • Assess gait. • Test muscle
4. Have you noticed yourself regularly bumping into things or having difficulty writing?				
 • Observe tandem gait and finger to nose.
5. Have you regularly been experiencing difficulty understanding others?				
 • Test ability to follow serial commands.
6. Have you had persistent problems with your memory or thinking?				
 • Recall of 3 objects over 1 minute with distraction (only if
7. Have you been experiencing any persistent numbness or other loss of sensation?				
 • Test sensation side to side with either pinprick or cold (only if

Appendix 8 Worksheet for the PML Neurologic Examination (cont.)

PML Objective Checklist

Neurologic function being assessed	Instructions (bold text indicates parts of exam required at each visit, as specified in Schedule of Assessments)	Abnormal exam?		If the answer is "Yes", describe the abnormal objective exam
		YES	NO	
1. Visual fields and ocular motility	
 Visual Field Testing Ocular Motility Testing 			
2. Speech	
 Observe the patient's speech output for dysarthria or aphasia. 			
3. Strength	
 Pronator drift test (Barre maneuver) Gait testing (normal, heel and toe walk) ONLY if the patient has any subjective complaints of weakness, test muscle strength of the relevant muscle groups 			
4. Coordination	
 Observe tandem gait and finger to nose 			
5. Comprehension	
 Test ability to follow serial commands "Take a piece of paper in your hand, fold it in half, and put it on the floor." 			
6. Memory and thinking	
 ONLY if the patient has subjective complaints about their memory or thinking, test the ability of the patient to recall 3 objects over 1 minute with distraction 			
7. Sensation	
 ONLY if the patient has subjective sensory complaints, evaluate relevant areas based on patient's subjective complaints by comparing left vs. right side sensation to cold (e.g. alcohol swab or cold stethoscope) or pinprick (e.g. broken Q-tip) 			

Please refer to the PML Algorithm in the Protocol Appendix for details.

- If there is an abnormal finding on the PML Subjective Checklist, this should be appropriately documented on the worksheet and in the eCRF.

Appendix 8

Worksheet for the PML Neurologic Examination (cont.)

- If there is an abnormal finding on the PML Objective Checklist, this should be appropriately documented on the worksheet and in the eCRF.
- If there are any abnormalities found on the PML Subjective Checklist that are accompanied by the corresponding abnormality on the PML Objective Checklist, or if there is high clinical suspicion for PML (in the opinion of the investigator):
 - This must be reported as an adverse event of special interest (AESI) within 24 hours
 - An urgent referral to a neurologist should be made.
 - Dosing with study drug will be suspended until PML can be ruled out.
 - Further evaluation will proceed according to the PML Algorithm in the Protocol Appendix.
 - Any confirmed diagnosis of PML should be reported as a serious adverse event (SAE).

Please complete the PML eCRF.

Was the PML Subjective Checklist administered? (Yes/No)

If yes, date of administration of PML Subjective Checklist (Date)

If yes, were there any abnormalities on the PML Subjective Checklist? (Yes/No)

Was the PML Objective Checklist administered? (Yes/No)

If yes, were there any abnormalities on the PML Objective Checklist? (Yes/No)

Is PML suspected? (Yes/No)

More detailed instructions for the PML Objective Checklist Neurologic Evaluations (please refer to the PML Neurologic Exam Video for more information):

1. Visual fields and ocular motility

Visual Field Testing:

- Position yourself approximately 3 feet away from the patient, with eyes at the same level.
- Keeping both eyes open, ask the patient to cover one eye and ask if all parts of your face and head are clear to them. Ask them to repeat, covering the other eye.

Appendix 8

Worksheet for the PML Neurologic Examination (cont.)

- Have the patient cover one eye and stare at your nose, and then ask them how many fingers you are holding up, testing each of the 4 visual quadrants. Repeat with the other eye covered.

Ocular Motility Testing:

- Evaluate the patient for conjugate eye movement.
- Starting about 3 feet from center, move in a big “H”, pausing at the center and at lateral gaze, and finishing with convergence (finger to their nose). Watch for nystagmus in lateral gaze, smooth pursuits, and pupillary constriction with convergence. Note: a couple of beats of nystagmus upon extreme lateral gaze is considered normal.

2. Speech

- Observe the patient’s speech output for dysarthria or aphasia.
- Dysarthria is a motor speech disorder. Findings can include “slurred” speech, decreased volume, slow rate of speech, limited tongue, lip, and jaw movement, abnormal rhythm when speaking, changes in vocal quality, and drooling or poor control of saliva.
- Aphasia is a disorder that results from damage to parts of the brain that control language, and can lead to problems with any or all of the following: speaking, listening, reading or writing.

3. Strength

Pronator drift test (Barre maneuver):

- Ask the patient to stand with their feet together and extend their arms out in front of them at 90 degrees (parallel to floor) with palms facing upwards toward the ceiling.
- Ask the patient to close their eyes and keep their arms extended for 15 seconds.
- If either arm drifts downward, upward, or starts to pronate (i.e. thumb turns up), this is considered an abnormal exam.

Gait testing:

- Ask the patient to walk across the room (~10 feet). The patient should have a normal gait, with their left arm swinging forward when the right foot leads, and vice versa. Be certain to note whether there is symmetric arm swinging, because a slight decrease in arm swinging may be an indicator of upper extremity weakness.
- Ask the patient to walk on their heels across the room (~10 feet). Carefully observe whether they have any difficulty maintaining their toes off the ground or loss of balance.

Appendix 8

Worksheet for the PML Neurologic Examination (cont.)

- Ask the patient to walk on their toes across the room (~10 feet). Carefully observe if they have any difficulty maintaining their heels off the ground or loss of balance.

Additional strength testing (ONLY if the patient has any subjective complaints of weakness):

- Test muscle strength of the relevant muscle groups based on the patient's subjective complaints.
- General guidelines for a basic muscle strength exam:
- Upper extremity:
 - Finger grip strength
 - Flexion at elbow
 - Extension at elbow
 - Deltoid strength: Maintain bent arms up (perpendicular to floor) and resist while investigator pushes down
 - Shoulder shrug against resistance
- Lower extremity: (examine while patient is sitting down)
 - Raise thigh (while bent)
 - Straighten leg
 - Flex leg
 - Flex foot
 - Extend foot

4. Coordination

Tandem gait:

- As the patient is looking at his feet, ask them to walk 8 steps with one foot touching in front of the other (demonstrate for them).

Finger to nose:

- Hold your finger out so they need to reach out and lean. Start near the center, and move your finger slowly so that they reach across their body. Make sure they alternate touching your finger and their nose at a good speed. Inability to perform this accurately is considered an abnormal test.

5. Comprehension

- Test ability to follow serial commands
- “Take a piece of paper in your hand, fold it in half, and put it on the floor.”

Appendix 8

Worksheet for the PML Neurologic Examination (cont.)

[figure not shown]
6. Memory and Thinking

- (ONLY if the patient has subjective complaints about their memory or thinking) test the ability of the patient to recall 3 objects over 1 minute with distraction.

7. Sensation

- (ONLY if the patient has subjective sensory complaints) evaluate relevant areas based on the patient's subjective complaints by comparing left vs. right side sensation to cold (e.g. alcohol swab or cold stethoscope) or pinprick (e.g. broken Q-tip). Confirm that the patient is able to feel the sensation symmetrically.

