4.4.4.5 Progressive Multifocal Leukoencephalopathy Assessment

Study site personnel and patients will be educated regarding the signs and symptoms of PML. New symptoms or signs suggestive of PML will be evaluated by a qualified HCP (e.g., investigator, physician assistant, nurse, nurse practitioner; a neurology consult is not required) with use of the PML Subjective Checklist (symptom assessment) and the PML Objective Checklist (neurologic evaluation; see [Appendix 8](#)) during Part 1 (OLE), 12-week safety follow-up, and Part 2 (SM) (see [Appendix 1](#), [Appendix 2](#), and [Appendix 3](#), respectively).

During Part 1 (OLE), the PML monitoring assessments will take place at Weeks 0 and 12 and every 12 weeks thereafter and at Study Completion (or Early Withdrawal visit).

If a patient has a positive finding on the PML Subjective Checklist that is accompanied by a positive finding on the PML Objective Checklist or if there is strong clinical suspicion for PML, the neurologic symptom or sign should be expeditiously reported to the Sponsor as adverse events of special interest or serious adverse events, as appropriate, within 24 hours (see Section [5.5.2](#) and [Appendix 9](#) for the Algorithm for Evaluation of Progressive Multifocal Leukoencephalopathy). If PML is suspected, dosing with etrolizumab for that patient will be suspended and the patient should be promptly referred to a neurologist.

Following formal evaluation by a neurologist, if PML cannot be ruled out, the case will be referred to an expert PML adjudication committee for further work-up, which may include brain magnetic resonance imaging (MRI) with and without contrast. If there remains any suspicion for PML, the PML adjudication committee may recommend performing a lumbar puncture with cerebrospinal fluid (CSF) analysis for JCV by polymerase chain reaction (PCR). If JCV is detected, the patient should be treated as a PML case, and the patient should permanently discontinue study drug and enter safety follow-up.

Dosing with study treatments can only be resumed in patients where PML has been ruled out. Refer to [Appendix 9](#) for the Algorithm for Evaluation of Progressive Multifocal Leukoencephalopathy.

After completing Part 1 (OLE), patients will enter the 12-week safety follow-up (see [Appendix 2](#)). The PML monitoring assessment is to be performed at Week 12 of this safety follow-up.

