During the etrolizumab treatment, patients should be closely monitored for any signs and symptoms of PML via regular (approximately once every 12 weeks) subjective and objective tests employing the use of checklists to assess the patient's mental and neurological status. These will comprise regular neurologic examinations (including evaluation of cranial nerves, motor and sensory function, coordination, and mental status) as per the Schedule of Assessments (see [Appendix 1](#)). The PML Subjective Checklist (symptom assessment) and the PML Objective Checklist (neurologic evaluation) will be administered ([Appendix 8](#); Worksheet for the PML Neurologic Examination) by a qualified HCP and will be performed as indicated on the Schedule of Assessments (see [Appendix 1](#)).

During the in-clinic visits, patients will undergo PML monitoring assessments.

If a patient has a positive finding on the PML Subjective Checklist that is accompanied by a positive finding on the PML Objective Checklist or if there is strong clinical suspicion for PML, the neurologic symptom or sign should be expeditiously reported to the

Sponsor as adverse events of special interest or serious adverse events, as appropriate, within 24 hours (see Section 5.5.2 and [Appendix 9](#) for the Algorithm for Evaluation of Progressive Multifocal Leukoencephalopathy).

If PML is suspected, dosing with study treatment for that patient will be suspended and the patient should be promptly referred to a neurologist. Following formal evaluation by a neurologist, if PML cannot be ruled out, the case will be referred to an expert PML adjudication committee for further work-up, which may include brain MRI with and without contrast. If there remains any suspicion for PML, the PML adjudication committee may recommend performing a lumbar puncture with CSF analysis for JCV DNA by PCR. If JCV DNA is detected, the patient should be treated as a PML case and the patient should permanently discontinue study drug and enter safety follow-up. Dosing with study treatments can only be resumed in patients where PML has been ruled out. Refer to [Appendix 9](#) for the Algorithm for Evaluation of Progressive Multifocal Leukoencephalopathy.

PML Treatment

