5.3.3 Adverse Events of Special Interest (Immediately Reportable to the Sponsor)

Adverse events of special interest are required to be reported by the investigator to the Sponsor immediately (i.e., no more than 24 hours after learning of the event; see Section 5.5.2 for reporting instructions). Adverse events of special interest for this study include the following:

- Cases of potential drug-induced liver injury that include an elevated ALT or AST in combination with either an elevated bilirubin or clinical jaundice, as defined by Hy's law (Section 5.4.6.7)
- Suspected transmission of an infectious agent by etrolizumab, as defined below:

Any organism, virus, or infectious particle (e.g., prion protein transmitting transmissible spongiform encephalopathy), pathogenic or non-pathogenic, is considered an infectious agent. A transmission of an infectious agent may be suspected from clinical symptoms or laboratory findings that indicate an infection in a patient exposed to a medicinal product. This term applies only when a contamination of the study drug is suspected.
- Adverse events of special interest specific to etrolizumab:

Systemic hypersensitivity reactions and anaphylactic and anaphylactoid reactions (see Section 5.1.1.2 and Clinical Criteria for Diagnosing Anaphylaxis in Appendix 10)

Neurological signs, symptoms, and adverse events that may suggest possible PML, on the basis of a positive finding on the PML Subjective Checklist that is accompanied by a positive finding on the PML Objective Checklist, or if there is strong clinical suspicion for PML (see Appendix 9 Algorithm for the Evaluation of Progressive Multifocal Leukoencephalopathy and Section 5.1.1.1)

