4.2.2 Adverse Events

Verbatim descriptions of AEs will be mapped to the latest version of the Medical Dictionary for Regulatory Activities (MedDRA).

Adverse events (AEs) will include all terms recorded on the AE Case Report Form (CRF) pages (except pregnancies). For each recorded AE, the term entered by the investigator describing the event (the “reported term”) will be assigned a standardized term (the “preferred term”) and assigned to a superclass term on the basis of the Medical Dictionary for Regulatory Activities (MedDRA) World Health Organization (WHO) dictionary of terms. All analyses of AE data will be performed using the preferred terms and system organ class unless otherwise specified.

For the etrolizumab program, the adverse events of special interest (AESIs) are the following:

- Systemic hypersensitivity reactions and anaphylactic and anaphylactoid reaction which will be reported using the MedDRA anaphylactic reaction Standard MedDRA Query (SMQ) algorithmic and Hypersensitivity SMQ narrow.
- Neurological signs, symptoms, and AEs that may suggest possible progressive multifocal leukoencephalopathy (see Appendices 5 and 6 of Protocol)
- Suspected transmission of an infectious agent by the study drug
- Cases of potential drug-induced liver injury that include an elevated alanine aminotransferase (ALT) or aspartate aminotransferase (AST) in combination with either an elevated bilirubin or clinical jaundice, as defined by Hy’s Law

Specific AEs listed below will also be reported:

- Serious infections
- Gastrointestinal Infections
- Opportunistic infections
- Malignancies

- Injection site reactions

A listing or, summary table (e.g., n > 10) of all AEs suspected or confirmed, and AEs associated with COVID-19 will be generated. Associated AEs are defined as all AEs reported within a time window of 7 days prior and 30 days after the confirmed COVID-19 start date (dates inclusive). Additionally, a listing of patients experiencing 'long COVID-19' will be generated. This listing will include all AEs with a duration >30 days occurring after a confirmed COVID-19 infection or a positive PCR test.

All AESIs and specific AEs will be determined using a selection of eCRF tick box or MedDRA SMQs, Adverse Events Group Terms (AEGTs), High Level Term (HLTs), High Level Group Terms (HLGTs), System Organ Class (SOC), as appropriate.

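### The Appendix 8 worksheet and Section 5.3.3 give different checklist triggers for reporting possible PML as an adverse event of special interest

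*Protocol*

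**What the plan says.** The protocol states the reporting trigger for possible PML in several places.

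- **Section 5.3.3**, which defines the AESIs, uses "a positive finding on the PML Subjective Checklist that is accompanied by a positive finding on the PML Objective Checklist", or strong clinical suspicion. Reporting is due within 24 hours.
- **Sections 4.4.4.5 and 5.1.1.1.1** use the same condition for 24-hour reporting, as an AESI or a serious adverse event: "If a patient has a positive finding on the PML Subjective Checklist that is accompanied by a positive finding on the PML Objective Checklist", again with strong suspicion as the alternative. Dose suspension is a separate sentence with its own condition: "If PML is suspected, dosing with etrolizumab for that patient will be suspended".
- **Appendix 8**, the worksheet completed at the examination, uses "any abnormalities found on the PML Subjective Checklist that are accompanied by the corresponding abnormality on the PML Objective Checklist", or high clinical suspicion in the investigator's opinion. It attaches three actions to this one trigger: the 24-hour AESI report, urgent referral to a neurologist, and suspension of dosing.
- **Section 5.4.6**, for Part 2, has sites record neurological abnormalities found on both checklists, or where suspicion is strong, each as a separate AESI.

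The PML eCRF fields shown in Appendix 8 hold one Yes/No answer per checklist, for example "were there any abnormalities on the PML Objective Checklist". They ask nothing about matching.

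SAP 4.2.2 lists the PML AESI as "Neurological signs, symptoms, and AEs that may suggest possible progressive multifocal leukoencephalopathy (see Appendices 5 and 6 of Protocol"). It identifies AESIs by eCRF tick box or by MedDRA-based groupings, and tabulates them for the Part 1 report.

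**The concern.** The definition in the body text is met by any pair of positive findings. The worksheet's checklist rule is met only by a matched pair. Appendix 8 gives *corresponding* a concrete meaning, because it prints the applicable objective test beside each question. Staff working from that page could reasonably take the matched pair as the rule.

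What is at stake is the completeness of one safety count. PML is the event for which the sponsor keeps up extensive monitoring, and the Part 1 report will present a PML AESI count that is likely to be low or zero. If some sites applied the matched rule, a zero would not show that no patient met Section 5.3.3. The checklist fields that could show it are collected, but SAP 4.2.2 plans no output from them.

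**Working it through.** The plan gives no figure to reproduce, so the check is a comparison of texts followed by an illustrative count.

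**Texts side by side**

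| Place | Checklist condition | Matching stated? | Alternative |
|---|---|---|---|
| 5.3.3 | Positive Subjective with positive Objective | No | Strong suspicion |
| 4.4.4.5, 5.1.1.1.1 | Same | No | Strong suspicion |
| Appendix 8 | Subjective with the corresponding Objective | Yes | High suspicion |
| 5.4.6 (Part 2) | Found on both lists | Unclear | Strong suspicion |

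**Can unmatched pairs occur?** Yes. Appendix 8 has the bolded Objective items done at every examination visit, whatever the patient reports.

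**Example.** A patient answers Yes only to question 7 (numbness). Sensation is normal on testing (Objective item 7), but tandem gait is abnormal (item 4). Both lists have a positive finding, so 5.3.3 is met on its plain wording. Appendix 8 pairs question 7 with sensation testing only, and its domain table puts question 7 under sensory deficits and question 4 under coordination. The worksheet's checklist condition is therefore not met under either pairing, and an AESI report depends on the suspicion route.

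**Count of combinations.** Take one positive item on each list. Assume that Objective items 1 to 5 are the bolded ones (the bold type is lost in the extract). Items 6 and 7 are tested only after the matching complaint.

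- Possible pairs: 7 questions × 5 items = 35, plus (6,6) and (7,7), gives 37. All 37 meet the checklist condition of 5.3.3 as worded.
- *Corresponding* read as the test beside the question: 7 pairs match, and 37 − 7 = 30 do not.
- *Corresponding* read as the same neurologic domain, using the Appendix 8 groups {2,5,6}, {1}, {2,3}, {7} and {4}: the 7 pairs plus (2,3), (2,5), (3,2), (5,2), (6,2) and (6,5) give 13, and 37 − 13 = 24 do not match.

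Under these two readings, 24 to 30 of the 37 combinations are classified differently. The example, (7,4), is among them in both cases.

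**The case against.** The strongest reply is that the texts are compatible. Appendix 8 says when a report must be made. It does not say that a report is made only then, so a site that follows 5.3.3 also complies with the worksheet. Section 5.3.3 speaks of a positive finding accompanied by another, which could be meant as one abnormality confirmed on examination, and 5.4.6 supports that reading. Both documents' wording leaves a suspicion route. Both 5.3.3 and Appendix 8 point to the Appendix 9 algorithm, whose figure is not shown here. A new sign should also be recorded as an adverse event in Part 1, the SAP's AESI selection is not limited to the tick box, and confirmed PML is a serious adverse event in any case.

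Most of this stands as a limit on the effect. Sites remain bound by 5.3.3, so an unmatched pair *might* go unreported; it cannot be said that it *will*. None of it removes the difference in wording. If matching was intended, 5.3.3 is the text that needs changing, and Appendix 9 could not delete the sentence in Appendix 8.

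The count is also open to challenge. A wider clinical reading of *corresponding* is possible. A visual-field defect may well explain a Yes to "Have you noticed yourself regularly bumping into things or having difficulty writing", and Appendix 8 lists "Loss of visual fields (homonymous hemianopsia), double vision (diplopia") among the visual signs of PML. Such a patient is also a natural case for high suspicion. So 24 is not a lower bound.

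**Conclusion.** The inconsistency is real and worth correcting, at modest priority. A site relying on Appendix 8 might not report as an AESI a patient who meets 5.3.3, unless suspicion is judged high. The number of patients affected cannot be derived from the documents. The combination count shows only that the two conditions differ widely on paper, and it rests on the assumption about bolded items and on two of several readings of *corresponding*.

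Three stronger readings are tempting, and the documents do not support them:

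- That the worksheet forbids reporting of unmatched pairs. It contains no such restriction.
- That PML cases would be lost. Confirmed PML is reported separately, and both checklist results are entered in the eCRF.
- That the SAP uses a different PML definition because it cites Appendices 5 and 6. Those hold the Crohn's Disease Activity Index and the Abdominal Pain Questionnaire, so the citation is a clerical slip.

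No planned statistical method changes.

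**What to change.** 1. **Protocol.** Use the 5.3.3 condition as the single AESI-reporting trigger in Appendix 8 and Section 5.4.6: any Subjective abnormality with any Objective abnormality, or strong clinical suspicion. State explicitly that the findings need not match. The worksheet ties referral and dose suspension to the same trigger as reporting, so the sponsor's clinicians should confirm whether those two actions follow the unified trigger.
2. **SAP, for the Part 1 report.** Add one listing of visits where the Subjective and the Objective abnormality fields are both Yes, flagging those without a PML AESI. The sponsor terminated Part 1 on 15 February 2022, with last dosing on 15 May 2022, so rewording the worksheet can do little for Part 1 data. The listing still can.
3. **Clerical.** In SAP 4.2.2, cite Protocol Appendices 8 and 9 in place of 5 and 6.

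The cost is a short protocol amendment with the approvals in Section 9.6, one listing from fields already collected, and one corrected reference. The downside is a few more AESI reports that prove negative, for example an old stable deficit alongside an unrelated new complaint.
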